## **7.4 Protocol Deviations**

Number and percentage of subjects who reported at least one of the following protocol deviation categories will be provided.

- Subject entered into the study even though she/he did not satisfy entry criteria
- Subject who developed withdrawal criteria during the study and was not withdrawn
- Subject who received wrong treatment or incorrect dose
- Subject who received excluded or prohibited concomitant treatment

## **8.0 Patient Disposition**

The number of subjects for each of the following categories will be summarized, overall and for each treatment group in the ITT population, overall and per study site:

- Number of subjects randomized
- Number of subjects randomized with prior phototherapy
- Number of subjects treated
- Number of subjects who completed the study
- Number of subjects who discontinued the study drug
- Number of subjects who prematurely discontinued study

In addition, the reasons for premature discontinuation (all reasons and primary reasons) will be summarized with frequencies and percentages.

Beyond patient disposition, number of screening failures and reasons for screening failure will also be summarized among all screened subjects in a subject screening status table.

## **9.0 Study Drug Exposure and Compliance**

Summary of study drug treatment duration and compliance will be provided for each treatment arm in the ITT Population.

Study drug treatment duration (days) will be summarized using the sample size, mean, standard deviation, minimum, first quartile, median, third quartile and maximum. Study drug treatment duration will be summarized as follows:

### **Risankizumab Exposure (in Days)**

Risankizumab Exposure (days) = Date of last injection – Date of first injection + 84 days.

### **FUMADERM® Exposure (in Days) [this includes FUMADERM® Initial]**

FUMADERM® Exposure (days) = Date of last dose of oral study drug – date of first dose of oral study drug + 7 days.

For subjects in the FUMADERM® group, there will also be the following analyses

- Interruption of FUMADERM® dosing of more than 7 consecutive days between first and last dose (yes, no)
- For subjects with an interruption of more than 7 consecutive days, total number of days without FUMADERM® dosing between first and last dose

In addition, the total dose of FUMADERM® (mg) and the average daily dose of FUMADERM® (mg) calculated as total dose divided by number of days with doses taken, will be presented. The presentation of average daily dose will be done overall as well as for each week separately.

### **Compliance**

For subjects in the Risankizumab group, there will be a summary of the number of subjects receiving study drug and dose at each study drug administration visit. This will be repeated on the cumulative number of doses.

For subjects in the Risankizumab group, when computing compliance at each study drug administration visit, the denominator will include all subjects in each analysis population who have not prematurely discontinued the study drug prior to the scheduled study drug

injection. Subjects who have prematurely discontinued the study drug but have not prematurely discontinued the study are not used in the denominator.

For subjects in the FUMADERM® group, for each visit (Week 4, 8, 12, 16, 20, 24), the number of subjects deviating from the pre-specified dosing schedule including reasons will be provided, including non-compliance.

## **10.0 Efficacy Analysis**

### **10.1 General Considerations**

The treatment effect will be evaluated based on a two-sided significance level of 0.05 (when rounded to three decimal places).

The ITT population will be used for the analyses of efficacy endpoints.

Subjects' prior phototherapy exposure will be used as the stratum in the stratified analyses.

#### **10.1.1 Analyses of Categorical Variables**

For categorical variables, frequencies and percentages will be summarized. Treatment comparison will be conducted using a Cochran-Mantel-Haenszel (CMH) test with the above stratification factor as stratum for the analysis. The CMH test will use weights proposed by Greenland & Robins, which is calculated as follows:

$$\hat{\delta}_{MH} = \frac{\sum_{i=1}^u w_i \cdot \hat{\delta}_i}{\sum_{i=1}^u w_i}, \text{ where}$$

$\hat{\delta}_i = \frac{x_i}{n_i} - \frac{y_i}{m_i}$  denotes the risk difference in stratum  $i, i = 1, \dots, u$

$w_i = \frac{n_i \cdot m_i}{n_i + m_i}$  denotes the weight of stratum  $i, i = 1, \dots, u$

$x_i$  denotes the number of subjects with event in treatment1 in stratum  $i, i = 1, \dots, u$

$y_i$  denotes the number of subjects with event in treatment2 in stratum  $i, i = 1, \dots, u$

$n_i$  denotes the number of subjects on treatment1 in stratum i,  $i = 1, \dots, u$

$m_i$  denotes the number of subjects on treatment2 in stratum i,  $i = 1, \dots, u$

The estimated variance of  $\hat{\delta}_{MH}$  is calculated as:

$$\widehat{var}(\hat{\delta}_{MH}) = \frac{\sum_{i=1}^u L_i}{(\sum_{i=1}^u w_i)^2}$$

$$\text{where } L_i = \frac{x_i(n_i - x_i) m_i^3 + y_i(m_i - y_i) n_i^3}{n_i \cdot m_i \cdot (n_i + m_i)^2}, i = 1, \dots, u$$

Assuming a normal distribution of  $\hat{\delta}_{MH}$ , an approximate 95% CI is given as follows, where  $z_{0.975}$  is the 97.5% quantile of the standard normal distribution:

$$CI = \left[ \hat{\delta}_{MH} \pm z_{0.975} \cdot \sqrt{\widehat{var}(\hat{\delta}_{MH})} \right]$$

Also, the approximate p-value can be calculated using the following:

$$\text{pvalue} = 2 \cdot \Pr \left[ Z > \left| \frac{\hat{\delta}_{MH}}{\sqrt{\widehat{var}(\hat{\delta}_{MH})}} \right| \right], \text{ where } Z \sim N(0, 1)$$

If there is a stratum for a treatment group that has 0 subjects in any cell in the contingency table, all cells from the stratum will be added by 0.1 in order to prevent dividing by 0 in the above equations, as suggested in Greenland & Robins.

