**8.1.2 Planned Methods of Statistical Analysis**

All statistical tests will be two-tailed. The statistical tests for the primary endpoint will be performed at the significance level 0.05. All  $P$  values will be rounded to 3 decimal places. Descriptive statistics will be provided. These include the number of observations, mean, standard deviation, minimum, median, quartiles and maximum for continuous variables, and counts and percentages for discrete variables. The analyses will be performed using SAS® (SAS Institute Inc., Cary, NC, USA).

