**8.1.4 Analysis of Efficacy**

All efficacy analyses will be performed in the ITT population.

The primary efficacy endpoint (PASI90 at Week 24) will be analyzed using a two-sided Cochran-Mantel Haenszel test stratified by prior phototherapy at level of significance 5%. Missing data will be imputed using non-responder imputation, i.e., a subject with missing PASI90 at Week 24 will be considered a non-responder in the primary analysis. Further sensitivity analyses for the primary endpoint may be specified in the SAP prior to database lock.

For the analysis of categorical secondary endpoints, the same statistical test as for the primary endpoint will be performed, missing data will be imputed using non-responder imputation. For the analysis of continuous secondary endpoints, two-sided two-way ANOVA with treatment and prior phototherapy as factors will be imputed using last observation carried forward (LOCF).

The order of the secondary endpoints does not reflect a ranking and secondary endpoints will not be used for confirmatory interpretation, thus no adjustment for multiplicity will be done.

Further details regarding the statistical analysis will be specified in the SAP.

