## **Rounding of Numeric Results**

Rounding will be performed for presentation of results. No rounding will be performed before or during analyses. The ROUND function of SAS will be used to round results.

When dichotomizing continuous variables from single observations, associated continuous variables will be rounded to 9 decimal points before applying the cutoff point to determine the response status (for example, percent change from baseline in PASI score will be rounded to 9 decimal places before comparing to 90%).

The mean, median and quartiles will be rounded for presentation to 1 decimal more than the data entered into the database. The standard deviation will be rounded to 2 decimal places more than the data entered into the database. The minimum and maximum values will be presented as entered into the database.

Probabilities will be rounded to 3 decimal places before assignment of statistical significance and will be presented in rounded format. Probabilities that round to zero or are reported by SAS as zero will be presented as "< 0.001." Probabilities that round to 1 or are reported by SAS as 1 will be presented as "> 0.999."

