## **10.2 Primary Efficacy Analysis**

The primary efficacy endpoint is the proportion of subjects with a  $\geq 90\%$  reduction from baseline in Psoriasis Area and Severity Index (PASI 90) at Week 24.

The primary null hypothesis is that risankizumab is not different from FUMADERM® in achieving  $\geq 90\%$  reduction from baseline in the Psoriasis Area and Severity Index score (PASI 90) at Week 24.

The primary endpoint will be analyzed in the ITT Population. The difference in proportion of subjects achieving PASI 90 between treatment arms will be estimated and tested using the two-sided Cochran-Mantel-Haenszel risk difference estimate stratified by prior phototherapy exposure at level of significance 5%.

Non-responder imputation will be used as the primary approach for missing values. LOCF and MI will be performed as sensitivity analyses.

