## **14.0                   Summary of Changes**

### **14.1                   Summary of Changes Between the Latest Version of Protocol and the Current SAP**

In Section 10.1.2 of this SAP, the strategy for analysis of continuous endpoints was further refined. The protocol had specified ANOVA with treatment group and stratification factor in the model. The SAP now clarifies that for change from baseline in PSS a stratified van Elteren test will be used. For other continuous variables, treatment groups will be compared using ANCOVA with treatment group, Baseline value, and stratification factor in the model. This modification was done to align the study with the other studies in the Risankizumab Psoriasis development program.

In Section 10.3, NAPSI was added as a secondary endpoint to make optimal use of the data collected for NAPPA-CLIN assessments.

---

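### The SAP's primary p-value is an unpooled Wald test, not the protocol's stratified CMH test; it runs at about 5.5–6.1% instead of 5% and is not listed as a change

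*SAP*

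**What the plan says.** Protocol 8.1.4 states that the primary endpoint "will be analyzed using a two-sided Cochran-Mantel Haenszel test stratified by prior phototherapy at level of significance 5"%. It gives no formula and leaves further detail to the SAP.

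SAP 10.1.1 also speaks of a CMH test, but what it defines is a weighted risk difference with the Greenland-Robins variance, a normal-theory 95% interval, and a p-value introduced by "Also, the approximate p-value can be calculated using the following". The p-value refers the estimate divided by its estimated standard error to the standard normal distribution. SAP 10.2 applies this to the primary endpoint, where the difference is to be "estimated and tested using the two-sided Cochran-Mantel-Haenszel risk difference estimate stratified by prior phototherapy exposure at level of significance 5"%.

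SAP 14.1 sets out what differs from the protocol. It says that "the strategy for analysis of continuous endpoints was further refined" and that NAPSI was added as a secondary endpoint. It does not mention the primary test.

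On rounding, SAP 6.0 says: "Probabilities will be rounded to 3 decimal places before assignment of statistical significance". SAP 10.1 repeats this for the efficacy tests. Protocol 8.1.2 says only that p-values "values will be rounded to 3 decimal places", not that significance is judged on the rounded figure.

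**The concern.** The CMH chi-square and a Wald test on the Mantel-Haenszel risk difference share a numerator but not a variance. CMH uses the variance that holds when the arms do not differ. The SAP's variance lets the two arms have different rates, which tends to make it smaller than the CMH variance when a difference is observed. At 110 subjects that is enough to lift the type I error above the stated level.

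This is the trial's only confirmatory test, so its 5% level is the one error rate that the plan undertakes to hold. The 95% interval built on the same standard error is correspondingly a little too narrow. Because the label is unchanged and SAP 14.1 is silent, a reader of the protocol and the list of changes would not learn that the test differs.

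**Working it through.** **Inputs.** 110 subjects, 55 per arm, 1:1, with 70% versus 35% assumed (protocol 8.2, SAP 4.3); at most 20% with prior phototherapy (protocol 8.3), i.e. up to 11 per arm; the weights, variance and 0.1 zero-cell rule of SAP 10.1.1. The documents give neither the actual stratum split nor a null response rate, so both are varied.

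**The plan's own figure (94% power).** With mean rate 0.525:
- null SE = `sqrt(0.525 × 0.475 × 2/55)` = 0.0952
- alternative SE = `sqrt((0.70 × 0.30 + 0.35 × 0.65)/55)` = 0.0892
- uncorrected chi-square: (0.35 − 1.96 × 0.0952)/0.0892 = 1.83, power 96.6%
- continuity-corrected: (0.35 − 1/55 − 1.96 × 0.0952)/0.0892 = 1.63, power 94.8%; 94% needs 54 per arm

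The stated 94% therefore fits the continuity-corrected calculation.

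**Which test the SAP formula is.** In each stratum, with T = n + m and r = x + y:
- The numerator is common to both tests: `w(x/n − y/m) = x − nr/T`.
- SAP variance term: `L = w²[x(n−x)/n³ + y(m−y)/m³]`, which is unpooled.
- CMH variance term: `V = nm·r(T−r)/[T²(T−1)]`, the null hypergeometric variance.

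With n = m, a = the average of p₁q₁ and p₂q₂, and d = p₁ − p₂, these become `L = (n/2)·a` and `V = [n²/(2n−1)]·(a + d²/4)`. V exceeds L on both factors, so for equal arms the SAP statistic is the larger one (apart from the zero-cell adjustment).

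**Worked example.** 22/44 + 6/11 versus 14/44 + 4/11 responders (28/55 versus 18/55):

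| Stratum | w | d | w·d | L (SAP) | V (CMH) |
|---|---|---|---|---|---|
| No prior phototherapy | 22.0 | 0.1818 | 4.0 | 5.136 | 5.379 |
| Prior phototherapy | 5.5 | 0.1818 | 1.0 | 1.318 | 1.429 |
| Sum | 27.5 | | 5.0 | 6.455 | 6.808 |

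- SAP: z = 5/√6.455 = 1.968, p = 0.049
- CMH: z = 5/√6.808 = 1.916, p = 0.055

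**Type I error.** All two-stratum outcomes were enumerated exactly under a common response rate of 20–80%, with the 0.1 rule applied to the SAP statistic.

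| Subjects (without + with prior phototherapy) | SAP Wald | CMH chi-square |
|---|---|---|
| 44+11 in each arm | 5.64–6.13% | 4.52–5.10% |
| 50+5 in each arm | 5.55–6.11% | 4.53–5.15% |
| 53+2 in each arm | 5.52–6.03% | 4.53–5.15% |
| 45+10 versus 43+12 | 5.66–5.83% | 4.78–5.03% |

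Over all equal splits from 53+2 to 44+11 per arm, the range is 5.5–6.1% for the SAP test and 4.5–5.15% for CMH. The size of the small stratum hardly matters; the cause is the unpooled variance at this total sample size.

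**At the planned effect (70% versus 35%), equal splits.** Power is 96.8–97.0% (SAP) against 96.1–96.2% (CMH). The tests disagree in 0.7–0.8% of trials, and the SAP 95% interval covers 93.9–94.4%. At the cited 75.9% versus 22.3% they disagree in about 0.001% of trials.

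**Rounding.** The SAP does not say whether a rounded p of exactly 0.050 counts as significant. If it does, rounding adds 0.0–0.45 percentage point to the SAP test's size; if it does not, rounding removes 0.0–0.4 point.

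**The case against.** - **Elaboration, not replacement.** The protocol names the test without a formula and defers detail to the SAP, and population, strata, weights and estimate are unchanged. That is fair as far as it goes. But a CMH test is a defined statistic with a null variance, the SAP gives no other p-value formula, and SAP 14.1 does list the comparable refinement for continuous endpoints.
- **Nothing is hidden.** The formula is printed in full, the SAP is to be signed before database lock, and one variance for test and interval makes them agree about zero. All true. Openness does not hold the level, however, and the interval proposed below has the same agreement.
- **The figures assume equal arms within strata.** Stratified blocks do not guarantee this. With 46+9 versus 43+12 the SAP size is about 5.7%, the disagreement at 70% versus 35% is 0.43% of trials, and the power cost is about 0.4 point. So the 6.1% upper end and the larger disagreement figures belong to equal splits, but the inflation remains.
- **CMH is not exact either.** It reaches 5.15% at some null rates, but stays close to 5%, whereas the SAP test exceeded 5% in every scenario examined.
- **The consequence is small.** The excess is 0.5–1.1 points two-sided, about half of it in risankizumab's favour, and the example needs an 18-point difference, about half the planned 35. This stands and limits the weight of the point.
- **The fix separates the main analysis from multiple imputation.** If the imputation analysis keeps the Greenland-Robins variance, the two will differ in variance method as well as in handling of missing data. This also stands, as a small price.

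**Conclusion.** The concern holds. The SAP's primary p-value is an unpooled Wald test carrying the CMH name, it is not declared in SAP 14.1, and its type I error is about 5.5–6.1% rather than 5%. This rests on 55 per arm, null response rates of 20–80% and equal stratum splits up to the 20% cap; the unequal splits checked fall inside the range. The inflation is modest and would matter only for a borderline result, which is unlikely at the planned effect. It should still be corrected, because it concerns the one confirmatory test and the remedy is cheap. The rounding ambiguity is a minor addition. The risk difference itself is sound as an estimate.

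**What to change.** In SAP 10.1.1 and 10.2:

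1. Take the primary p-value from the stratified CMH chi-square (no continuity correction), as protocol 8.1.4 specifies.
2. Compare the unrounded p-value with 0.05 and round only for display.
3. Keep the Mantel-Haenszel risk difference as the estimate. For its 95% interval use the stratified Miettinen-Nurminen score interval with the same weights and the N/(N−1) factor. At a difference of zero its statistic is algebraically the CMH statistic, so p-value and interval cannot disagree about zero. Over all tables in four splits (53+2, 51+4, 47+8 and 44+11 per arm) there were no mismatches, and coverage at 70% versus 35% was 94.8%.
4. Use the same method for the categorical secondary endpoints, for consistency only. The multiple-imputation analysis pools the risk difference and can keep the Greenland-Robins variance.
5. List the new interval in SAP 14.1.

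Listing and justifying the present formula in SAP 14.1 would settle the disclosure but would not restore the 5% level.

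The cost is SAP wording, one standard procedure and an interval that must be solved iteratively. At 70% versus 35%, power falls by about 0.7–0.8 point for equal splits (about 96.9% to 96.1%) and about 0.4 point for the most unequal split checked. Borderline p-values become slightly less favourable.

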**Figure 1. Study Design Schematic**

**4.3 Sample Size**

Using a two-sided Chi squared test at level of significance 5%, the sample size of 110 (2 × 55) subjects will provide 94% power assuming response rates of the primary endpoint (PASI 90 at Week 24) of 70% for risankizumab and 35% for FUMADERM®.

These assumptions are in line with what has been observed in recent studies for risankizumab (63/83 (75.9%) at Week 24) and FUMADERM® 61/273 (22.3%) of the subjects achieved PASI 90 at Week 16 in the FUMADERM® arm in the BRIDGE trial.

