**5.2 Variables Used for Stratification of Randomization**

Subjects will be randomized in 1:1 ratio to receive risankizumab or FUMADERM® stratified by prior phototherapy, with a maximum of 20% of subjects with prior phototherapy. Randomization will not be stratified by center due to the limited number of subjects per center. Randomization will be done using an adequate block size.

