**10.5 Efficacy Subgroup Analysis**

To evaluate the consistency of the efficacy over demographic and other baseline characteristics, summaries and analyses will be performed for the following subgroups for the primary efficacy endpoint.

- Age (< 40 years,  $\geq 40$  –  $< 65$  years,  $\geq 65$  years)
- Sex (male, female)
- Race (white, non-white)
- Smoking (current, former or never)
- BMI (normal:  $< 25$ , over weight:  $\geq 25$  –  $< 30$ , obese:  $\geq 30$ )
- Baseline PASI score (by median)
- Baseline sPGA ( $\leq 2, 3, 4$ )
- Prior Phototherapy (yes/no)

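### SAP 10.5 leaves the Wald Mantel-Haenszel risk difference of 10.1.1 as the only method for subgroup levels of any size, and in sparse levels its intervals and p-values are not valid

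*SAP*

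**What the plan says.** SAP 10.5 aims to judge whether the effect is consistent over baseline characteristics: "summaries and analyses will be performed for the following subgroups for the primary efficacy endpoint". The factors are age (3 levels), sex (2), race (2), smoking (2 or 3, depending on how the entry is read), BMI (3), baseline PASI split at the median (2), baseline sPGA (3) and prior phototherapy (2), which makes 19 or 20 levels. The section gives no method, minimum size, pooling rule, interaction assessment or statement that the results are descriptive.

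The method has to come from the general efficacy rules. SAP 10.1 sets a two-sided 0.05 level and uses prior phototherapy as the stratum. SAP 10.1.1 gives the Mantel-Haenszel risk difference, its variance, a 95% interval from the normal quantile, and a p-value from the estimate divided by its standard error. If a stratum has a zero cell, "all cells from the stratum will be added by 0.1 in order to prevent dividing by 0 in the above equations".

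SAP 10.4 declines multiplicity adjustment for secondary endpoints and does not mention subgroups. Elsewhere the SAP uses exact methods for sparse counts: Fisher's test for baseline tables with an expected count below 5 (7.1) and for adverse events (11.1).

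**The concern.** A Wald interval for a difference of proportions relies on a variance estimated from the observed cells. When nearly everyone in one arm responds, or nearly no one in the other does, that variance collapses and the result looks far more precise than the data allow. Adding 0.1 to each cell keeps the standard error above zero but leaves it very small.

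The trial plans 110 subjects, so the outer levels of some factors could hold only a few per arm. A table meant to show consistency could then contain rows with very small p-values and impossible confidence limits from four to six patients. Readers could take these as evidence of effect, or of difference between subgroups, when they are products of the formula.

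**Working it through.** **The plan's own figure.** SAP 4.3 says that 110 (2 × 55) "subjects will provide 94% power assuming response rates of the primary endpoint" of 70% and 35%. The uncorrected formula gives 96.6% and the continuity-corrected formula 94.8%. Exact enumeration with the Yates-corrected or Fisher test gives 94.2%. The stated 94% therefore reproduces with a continuity correction or an exact test. It says nothing about subgroups.

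**Inputs.** Estimator, variance, p-value and zero-cell rule: SAP 10.1.1. Two-sided 0.05: SAP 10.1. Stratum sizes: SAP 5.2, "Subjects will be randomized in 1:1 ratio to receive risankizumab or FUMADERM® stratified by prior phototherapy", with prior phototherapy capped at 20%. That is at most 0.20 × 110 = 22 subjects, about 11 per arm. All other level sizes below are assumptions.

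**Formula.** With one stratum, the 10.1.1 variance reduces to x(n − x)/n³ + y(m − y)/m³.

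**2/2 vs 0/2.** The cells become 2.1 and 0.1 against 0.1 and 2.1, with n = m = 2.2.
- Difference = 2.0/2.2 = 0.909.
- Variance = 2 × (2.1 × 0.1)/2.2³ = 0.42/10.648 = 0.0394, so SE = 0.199.
- z = 4.58, p = 0.000005, 95% CI 0.52 to 1.30. Fisher gives 0.33.

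The four subjects may all lie in one phototherapy stratum. The rule can be read as patching the other, empty stratum too. That stratum then has weight 0.2 × 0.2/0.4 = 0.1, difference 0 and L = 0.025.
- Difference = (1.1 × 0.909)/1.2 = 0.833.
- Variance = (1.1² × 0.0394 + 0.025)/1.2² = 0.0505, so SE = 0.225 and p = 0.0002.

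**3/3 vs 1/3.** n = m = 3.2.
- Difference = 2/3.2 = 0.625.
- Variance = (3.1 × 0.1 + 1.1 × 2.1)/3.2³ = 2.62/32.768 = 0.0800, so SE = 0.283.
- p = 0.027, 95% CI 0.07 to 1.18. Fisher gives 0.40.
- With an empty second stratum patched: difference = 1.0/1.7 = 0.588, variance = (1.6² × 0.0800 + 0.025)/1.7² = 0.0795, p = 0.037.

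**False-positive rate.** This is an exact enumeration in one stratum with the same true response rate in both arms. As a check by hand, take 3 per arm at 50%. The rejecting tables are 3 vs 0, 3 vs 1, 2 vs 0 and their mirror images, with probability 2 × (1 + 3 + 3)/64 = 21.9%.

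| Per arm | 20% | 35% | 50% | 70% |
|---|---|---|---|---|
| 3 | 11.3% | 19.3% | 21.9% | 17.2% |
| 4 | 2.4% | 5.7% | 7.0% | 4.7% |
| 5 | 4.4% | 9.2% | 10.9% | 7.8% |
| 11 | 9.1% | 6.9% | 5.8% | 7.7% |

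The rate does not fall steadily with size because the tables are so discrete. Fisher's test stays at or below about 2% at 3 and 5 per arm. A simulation with two strata (assuming 20% with prior phototherapy, true rates 35-70%) gave 11-16% for level totals of 4 to 10, 9-10% at 22 and about 6.7% at 55.

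**Which part is responsible.** If zero cells are left unpatched and a zero standard error with a non-zero difference counts as a rejection, the rates are the same at 2, 3, 5, 8 and 11 per arm. At 4 per arm they are higher, 15-18% against 2-7%. Adding 0.5 instead lowers the rate at 3 per arm to 1-3% but changes nothing at 2, 4 or 5. The source is therefore mainly the Wald approximation.

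**Primary analysis.** With 44 + 11 per arm, a zero cell arises in about 0.2-2.8% of trials and the false-positive rate is about 5.8%.

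**The case against.** The strongest reply is that SAP 10.5 orders no test in each level. It speaks of summaries and analyses, its aim is consistency, there is one primary hypothesis, and even secondary endpoints are non-confirmatory. This stands in part. A p-value per level is an inference, but 10.1 and 10.1.1 are the only rules available. The intervals would be wrong even without p-values.

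Second, the documents give no expected counts for non-white subjects, those aged 65 or older, or sPGA 2 or less. This stands: the rates at 3 and 5 per arm are conditional on such levels being that small. Prior phototherapy is the only level whose size the plan bounds.

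Third, the zero-cell rule has a purpose. For 2/2 vs 0/2 the unpatched variance is zero, and the p-value equation divides by its square root. This also stands, although many zero-cell tables would not need the patch. The patch makes 3/3 vs 1/3 less extreme (p = 0.014 unpatched, 0.027 patched).

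A reader might also infer that one responder against one non-responder is declared significant. That is not a reliable result of the SAP: p = 0.0195 if the empty phototherapy stratum is skipped and 0.060 if it is patched, and the text does not say which applies.

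**Conclusion.** The point holds for the subgroup tables. Applied as written, the 10.1.1 method gives misleading intervals and p-values in sparse levels: in a single stratum, roughly two to four times the nominal error at 3 per arm, up to about twice at 5, and 6-9% at the largest size that the phototherapy cap allows. The examples of 2/2 vs 0/2 and 3/3 vs 1/3 stay below 0.05 however an empty stratum is handled.

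This rests on two assumptions: that some levels will be small, and that 10.1.1 governs 10.5. Two stronger readings are not supported. The first is that the 0.1 constant is the cause and that removing it would cure the problem; the enumeration shows otherwise. The second is that the primary conclusion is at risk; it is barely touched. This is a risk of misinterpreting subgroups, worth correcting before database lock.

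**What to change.** In SAP 10.5:
- report responder counts and an unstratified score (Miettinen-Nurminen) or exact 95% CI for the risk difference in each level;
- give no per-level p-values;
- show counts only where either arm has fewer than 5 subjects;
- label all subgroup results descriptive.

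A treatment-by-subgroup interaction estimate may be added as a descriptive aid, on the understanding that 110 subjects give it little power.

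In SAP 10.1.1, add only that a stratum with no subjects in one arm is dropped. Do not change the rule to leave zero cells as observed. With the Wald formula that gives zero variance in tables such as 2/2 vs 0/2. It gives 0/0 for any endpoint with no responders in either arm, which could happen with PASI 100 at Week 4.

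The cost is a few sentences and minor programming. The intervals will be wider and fewer subgroup rows will look significant.
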